## 4.4 Treatment Group Assignment

The dose escalation portion of the study carries a traditional 3+3 design to evaluate three dose levels of PF-07901800. Standard guidelines for enrollment for the 3+3 design will be followed, with requirement that three

Pfizer Inc. / Protocol: TTI-621-03/C4961003  
IQVIA Biotech (Confidential) Project # YXA42460

patients complete the 21-day safety assessment period before the next dose cohort is open to enrollment and expansion to six patients in the case of a treatment-related dose-limiting toxicity.

However, recognizing that leiomyosarcoma is a rare disease and expecting that patients with leiomyosarcoma may be eager to participate in the study, careful modifications to the enrollment schema have been developed to avoid having to withhold enrollment for these patients.

During the dose escalation portion of the study, eligible patients will be enrolled to the cohort that is open at the time they present to the study. Based on known safety and clinical activity of the lowest planned dose of PF-07901800, 0.2 mg/kg, gleaned from other ongoing clinical trials, it is anticipated that this dose will serve as the PF-07901800 dose level for Cohort A. Thus, expansion Cohort A will open to enrollment once that dose level is judged to be safe in the dose escalation portion of the study; if a dose escalation cohort and expansion Cohort A are open to enrollment at the same time, priority for enrollment will be given to the dose escalation cohort and enrollment into expansion Cohort A will be limited to those patients who present to the study after enrollment to an escalation cohort is closed and meet all the eligibility criteria for the expansion portion of the study (including documentation of the leiomyosarcoma indication).

When both expansion cohorts are open to enrollment, assignment of eligible patients will be made on an alternating basis, with cohort assignment made by the CRO overseeing the study on behalf of the sponsor independent of investigator input and based strictly on chronology of verification of eligibility of patients as they complete screening assessments.

#### 4.5 Assessment Schedule

The study participation for a patient might include the Screening Visit (Day -28 to -1); Cycle 1 (21-days cycle), Day 1 and Day 8; Cycle 2 to 6 (21-days cycles), Day 1 and Day 8 ( $\pm$  1 day); Subsequent Cycles (28-days cycles), Day 1 and Day 15 ( $\pm$  3 days); 7 ( $\pm$  3 days) after last administration of study treatment; Safety Follow-up Period (30 + 5 days after last administration of study treatment or before initiation of subsequent anti-cancer therapy, whichever occurs soonest); and Long-Term Follow-Up, assessed every 12  $\pm$  2 weeks.

The protocol provides additional details in Section 11.

Pfizer Inc. / Protocol: TTI-621-03/C4961003  
IQVIA Biotech (Confidential) Project # YXA42460

## 5. Interventions

### 5.1 Study Procedures

Written informed consent must be granted by each patient prior to the initiation of any study procedure or assessment, including assessment of histology.

The study will consist of a 28-day screening period, a treatment period in which patients will receive doxorubicin in combination with PF-07901800 in 21-day cycles for a maximum of six cycles, followed by continued treatment with PF-07901800 as monotherapy in 28-day cycles until documentation of objective disease progression or development of unacceptable toxicity, and a long-term follow-up period for assessment of overall survival.

Serial blood samples will be obtained at baseline, during and after treatment for assessment of PF-07901800 pharmacokinetic and pharmacodynamic endpoints, as well as CCI [REDACTED]. End-of-Treatment (under protocol V1 only), Safety Follow-up and Long-Term Follow-Up Assessments will be performed.

Tissue biopsies will be collected during the screening period and after Cycle 2 for patients enrolled in the expansion cohorts; optional biopsies at the time of response and progression will be offered to patients.

The protocol v2.0 provides additional details on the activities and timing in Section 10, table 24 through 27.

## 6. General Analytical Considerations

### 6.1 Study Summaries and Tabulations

The definition of “treatment group” will be tabulated as follows:

- Dose escalation cohorts (Phase 1)
  - Dose 1 (0.2 mg/kg)
  - Dose 2 (0.7 mg/kg)
  - Dose 3 (2.0 mg/kg)
- Expansion cohorts (Phase 2)
  - Cohort A (0.2 mg/kg)
  - Cohort B (1.0 mg/kg)
  - Cohort C (2.0 mg/kg)
- Pooled cohorts by dose level
  - Lower dose (0.2 mg/kg)

Pfizer Inc. / Protocol: TTI-621-03/C4961003  
IQVIA Biotech (Confidential) Project # YXA42460

- Higher dose (2.0 mg/kg)
- Overall
  - Phase 1 total
  - Phase 2 total
  - Phases 1 + 2 total (for non-efficacy summaries only)

Data will be summarized by treatment group as above, as applicable.

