### 4.3.2 Expansion cohorts

Expansion cohorts are initially planned to evaluate two PF-07901800 dose levels in combination with doxorubicin: a low dose of PF-07901800 (Cohort A) and a higher dose (Cohort B). A Simon two-stage design will be used for each dose cohort, assuming a baseline overall response rate of 10% with doxorubicin monotherapy in the Simon two-stage design and an alternative of 25%, a power of 90% and one-sided Type 1 error set at 0.20, each dose level cohort will require 18 patients enrolled and evaluable for response in Stage 1; with at least two clinical responses, an additional 13 patients will be enrolled in Stage 2. The combination will be considered worthy of further study if at least five clinical responses are observed in either 31-patient cohort.

To mitigate the risk of thrombocytopenia Grade 3 or Grade 4 observed at PF-07901800 highest dose 2mg/kg (Cohort B) on Day 8 during the combination therapy, PACL No 5 was issued to terminate enrollment into Cohort B after enrollment of the 18 patients (Stage 1) was completed. The remaining 13 patients, who were initially planned to be enrolled in Stage 2 Cohort B, were enrolled in an expansion Cohort C which was added to the study to evaluate a medium dose of PF-07901800 at 1 mg/kg. Simon's 2-stage design was not applicable for Cohort C.

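### SAP 6.1 and SAP 4.3.2 give Cohorts B and C opposite doses; tables filled by cohort letter would show 31 patients under the other cohort's dose

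*SAP*

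**What the plan says.** SAP 6.1 sets out what treatment group means for the whole analysis. Under the expansion phase it lists Cohort A at 0.2 mg/kg, then "Cohort B (1.0 mg/kg" and "Cohort C (2.0 mg/kg" (the closing brackets are left off here). Below that, under "Pooled cohorts by dose level", it defines a lower-dose group at 0.2 mg/kg and a second group, "Higher dose (2.0 mg/kg". It does not say which cohorts make up either pooled group.

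SAP 4.3.2 tells how the expansion cohorts came about. Grade 3 or 4 thrombocytopenia was seen at "PF-07901800 highest dose 2mg/kg (Cohort B) on Day 8 during the combination therapy", and a letter was issued to "terminate enrollment into Cohort B after enrollment of the 18 patients (Stage 1) was completed". It goes on: "The remaining 13 patients, who were initially planned to be enrolled in Stage 2 Cohort B, were enrolled in an expansion Cohort C". That cohort is described as "an expansion Cohort C which was added to the study to evaluate a medium dose of PF-07901800 at 1 mg/kg".

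SAP 8 (efficacy), SAP 9 (safety) and SAP 9.3 (TEAE tables) all refer back to Section 6.1 for their groups.

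**The concern.** The two sections pair the same letters with opposite doses. Section 6.1 is not background: it is the definition from which the table columns are built. A programmer following it has two instructions that disagree, and the SAP does not say which prevails.

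The expansion cohorts exist to describe activity and tolerability at each dose. The outputs at risk include the objective response rate, which is the primary efficacy endpoint, and thrombocytopenia, which is an adverse event of special interest and the stated reason Cohort B was closed. If the swap carries into the tables, a reader would see the thrombocytopenia from the cohort closed for it at the wrong dose, and the response rates for B and C reversed by dose.

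**Working it through.** **The two sections side by side**

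| Cohort | Dose in SAP 6.1 | Dose in SAP 4.3.2 | Patients (SAP 4.3.2) |
|---|---|---|---|
| A | 0.2 mg/kg | low dose; 0.2 mg/kg anticipated in SAP 4.4 | not stated as enrolled; 31 planned |
| B | 1.0 mg/kg | 2 mg/kg | 18 |
| C | 2.0 mg/kg | 1 mg/kg | 13 |

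Two of the three expansion labels conflict.

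**Does any other text settle it?** Protocol 12.1.2 and the opening of SAP 4.3.2 call Cohort B the higher-dose cohort. Protocol 5.2.3 plans the high dose as 2.0 mg/kg but allows a different one. These fit the account in 4.3.2 more easily than 6.1, but they describe a plan, and version 2.0 of the protocol has no Cohort C. SAP 4.2 and SAP 9.1 still describe two expansion cohorts or dose levels. No passage corrects either section.

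**Counts**

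- Planned expansion total: 2 × 31 = 62 (SAP 4.2). The composition implied by 4.3.2, with Cohort A at its planned size, gives the same figure: 31 + 18 + 13 = 62.
- Patients in Cohorts B and C: 18 + 13 = 31.
- Share of the planned expansion: 31 / 62 = 50%.

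**What each way of filling the columns would show, taking 4.3.2 as the reference**

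- By cohort letter: the 18 Cohort B patients appear under 1.0 mg/kg and the 13 Cohort C patients under 2.0 mg/kg. That is 31 of 31 under the other cohort's dose.
- By recorded starting dose: 0 of 31 under the wrong dose, but the 18 patients at 2 mg/kg are headed Cohort C and the 13 at 1 mg/kg are headed Cohort B.

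**The pooled 2.0 mg/kg group.** If its members are selected by dose, it is unaffected. If they are selected through the 6.1 cohort labels, it takes in the 13 Cohort C patients and omits the 18 Cohort B patients. The number enrolled at escalation Dose 3 is not given; under the 3+3 design I assume 3 to 6.

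- Using the 6.1 labels: 3 + 13 = 16 to 6 + 13 = 19 patients.
- Using the 4.3.2 doses: 3 + 18 = 21 to 6 + 18 = 24 patients.

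**Not affected.** Cohort A, the escalation groups, the pooled lower dose and the phase totals do not depend on the B and C labels. Nor do the DLT tables, since SAP 6.7.3 limits that set to the escalation cohorts.

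**The case against.** The strongest reply is that the SAP leans towards filling columns by dose, so the harmful case may never arise. SAP 6.7.1 classifies patients by treatment actually received, and its rules for wrong or reduced doses refer to planned or actual dose, never to a cohort letter. SAP 6.8 says most tables will have dose group in the columns. The pooled groups are defined by dose level. The detailed history in 4.3.2 is there for any programmer to read. The waterfall plot coloured by dose administered (SAP 8.3) and the dosing listings (SAP 9.1) would disagree with swapped tables. All outputs are descriptive.

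Much of this stands. It makes the letter-based error less likely and easier to notice, and it is why the count of 31 is conditional. It does not remove the conflict:

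- For a single wrong dose, and for dose reductions in the safety analysis, SAP 6.7.1 falls back on the initial planned dose. The planned dose for B and C is exactly what 6.1 and 4.3.2 dispute.
- A dose recorded at a later visit does not identify the cohort. Protocol Table 10 takes a patient from 2.0 to 1.4 to 1.0 mg/kg in two reductions. For the same reason, the accurate statement is that patients would be shown under a dose 4.3.2 does not assign to their cohort, not that they never received it.
- Even with every patient correctly placed by dose, the column headings would carry letters that contradict 4.3.2.

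A further fair point is that 31 of 62 is a planning proportion. Replaced patients who were dosed stay in the full analysis set, so the final column counts may differ from 18 and 13.

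**Conclusion.** The contradiction is real and lies in current SAP text, in the section that defines the table columns. It should be resolved before any by-cohort output is programmed or released.

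The size depends on how columns are filled: 31 patients (50% of the planned expansion) under the other cohort's dose if filled by letter, or no patients misplaced but two cohort letters in conflict with 4.3.2 if filled by starting dose. The pooled 2.0 mg/kg group is at risk only if its members are chosen through the 6.1 labels.

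The count takes the enrolment figures in 4.3.2 at face value; the 50% also rests on the planned total of 62. No hypothesis test or decision rule uses the labels. This review does not decide which section has the doses right; the trial's own records must do that.

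**What to change.** Reconcile SAP 6.1 with SAP 4.3.2 against the cohort assignment records and the starting doses in the dosing records, and correct whichever section is wrong. In 6.1, name the escalation and expansion cohorts that belong to each pooled dose group. Check the table shells against the corrected list and align any that carry the wrong pairing. The classification rules in SAP 6.7.1 can stay as they are.

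The cost is SAP wording and, where needed, table-shell headings: no patients, no new data and no change to any analysis method.

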## 6.2 Data Sources

All reported study data will be recorded on the electronic case report forms (eCRF) using Medidata Rave. During the data collection process, automated quality assurance programs will be used to identify missing data, out-of-range data, and other data inconsistencies. Lab data (chemistry and hematology) will come from local labs through the EDC.

## 6.3 Definition of Baseline

Baseline is defined as the last measurement taken prior to the first infusion of study medication (Cycle 1 Day 1).

The average of the pre-infusion results will be considered as the baseline value for vital signs taken at different timepoints on the same pre-infusion day.

## 6.4 Definition of on-treatment period

Safety endpoints will be summarized based on the on-treatment period, unless otherwise specified.

On-treatment period is defined as the time from the first dose of study treatment through minimum (30 days + last dose of study treatment, start day of new anti-cancer therapy captured on the “Survival Status” CRF).

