**13.1.2. Serious Adverse Event**

A serious adverse event is an adverse event occurring during any study at any dose of the investigational product(s) that fulfills one or more of the following:

- Results in death

- Is immediately life-threatening (the subject was at risk of death at the time of the event; this does not refer to an event which hypothetically might have caused death if it were more severe)
- Requires in-patient hospitalization or prolongation of existing hospitalization
- Results in persistent or significant disability or incapacity
- Results in a congenital abnormality or birth defect
- Is an important medical event that may jeopardize the patient or may require medical intervention to prevent one of the outcomes listed above

Medical or scientific judgment should be exercised in deciding whether reporting is appropriate in other situations, such as important medical events that may not be immediately life threatening or result in death or hospitalization but may jeopardize the patient or may require medical or surgical intervention to prevent one of the other outcomes listed in the above definition. These should also be considered serious.

Examples of such events include invasive or malignant cancers, intensive treatment in an emergency room or at home for allergic bronchospasm, blood dyscrasias or convulsions that do not result in hospitalization, or development of drug dependency or drug abuse.

All serious adverse events that occur after any patient has signed informed consent, been enrolled, before treatment, during treatment, or within 30 days following the cessation of treatment, whether or not they are related to the study intervention, must be recorded on a Serious Adverse Event form.

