#### 13.5.3. Time Period and Frequency for Collecting AE and SAE Information

The time period for actively eliciting and collecting AEs and SAEs (“active collection period”) for each patient begins from the time the patient provides informed-consent, which is obtained before undergoing any study-related procedure and/or receiving study intervention, through and including a minimum of 30 calendar days after the last administration of the study intervention.

For patients who are screen failures, the active collection period ends when screen failure status is determined.

If the patient withdraws from the study and also withdraws consent for the collection of future information, the active collection period ends when consent is withdrawn.

If a patient permanently discontinues or temporarily discontinues study intervention because of an AE or SAE, the AE or SAE must be recorded on the CRF and the SAE reported using the CT SAE Report Form.

Investigators are not obligated to actively seek information on AEs or SAEs after the patient has concluded study participation. However, if the investigator learns of any SAE, including a death, at any time after a patient has completed the study, and they consider the event to be reasonably related to

the study intervention, the investigator must promptly report the SAE to Pfizer using the CT SAE Report Form.

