#### **13.5.4. Documentation**

All AEs (serious and non-serious) occurring within the period of observation for the study must be documented in the CRF with the following information, where appropriate. (The period of observation for the study is described in [Section 13.5.3](#)).

- AE name or term
- When the AE first occurred (start date)
- When the AE stopped (stop date or an indication of “ongoing”)
- Severity of the AE
- Seriousness (hospitalization, death, etc.)
- Actions taken
- Outcome
- Investigator opinion regarding the AE relationship to the IP(s)

All nonserious AEs and SAEs occurring in a patient during the active collection period which begins after obtaining informed consent as described in [Section 13.5.3](#), will be recorded on the AE section of the CRF.

The investigator or designee is to record on the CRF all directly observed and all spontaneously reported AEs and SAEs reported by the patient.

The investigator must record his or her reasoning for this decision in the patient’s medical record and as a comment on the CRF

Reporting of AEs and SAEs for patients who fail screening are subject to the CRF requirements as described in [Section 13.5.3](#).

As part of ongoing safety reviews conducted by the sponsor, any nonserious AE that is determined by the sponsor to be serious will be reported by the sponsor as an SAE. To assist in the determination of case seriousness, further information may be requested from the investigator to provide clarity and understanding of the event in the context of the clinical study.

If a patient begins a new anti-cancer therapy, the recording period for nonserious AEs ends at the time the new treatment is started; however, SAEs must continue to be recorded on the CRF during the above indicated active collection period. Note that a switch to a commercially available version of the study intervention is considered as a new anti-cancer therapy for the purposes of SAE reporting.

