### 9.3 Adverse Events

Adverse events (AEs) will be documented on the AE eCRF and monitored continuously throughout the study. Adverse events will be coded using the Medical Dictionary for Regulatory Activities (MedDRA), latest version, associating lower-level terms with PT and SOC by the primary hierarchy.

Treatment Emergent Adverse Events (TEAEs) are those events with onset date occurring during the on-treatment period. The tables will display counts and percentages of patients who reported at least one TEAE in each SOC represented in the AE data. Within each SOC, the tables will display the counts and percentages of patients reporting at least one TEAE, as designated by the PT.

The severity of adverse events will be graded using the NCI Common Toxicity Criteria for Adverse Events (CTCAE version 5.0). The intensity is assigned a grade of 1 through 5 using the following CTCAE guidelines: Grade 1 – Mild; Grade 2 – Moderate; Grade 3 – Severe; Grade 4 – Life-threatening; Grade 5 – Death.

The causality of AE are reported as either related to study drug or not related to study drug for each study drug. Related AEs are those related to any study drug (i.e., at least one of the study drugs).

Pfizer Inc. / Protocol: TTI-621-03/C4961003  
IQVIA Biotech (Confidential) Project # YXA42460

If a patient has multiple occurrences of an adverse event, the strongest level of relationship to study drug(s) and the worst toxicity grade a patient experiences for a given AE will be used in these tables. No imputation will be performed for missing toxicity grade or causality data.

AEs that have missing onset dates will be considered as TEAE unless the stop date is known to be prior to the first administration of the study medication. If the AE onset date is partial, the date will be correlated as far as possible with the date of first dose of study medication. AE will be assumed to be TEAE, unless there is clear evidence (through comparison of partial dates) to suggest that the adverse event started prior to the first dose of study medication. Detailed imputation rules can be found in section 6.3. If patients died during the study and experienced AEs at the time of death, the AEs that lead to death will use death date as the AE end date; otherwise, AEs that do not lead to death will be reported as ongoing.

Adverse Events of Special Interest (AESI) include the following:

- Thrombocytopenia: Haematopoietic thrombocytopenia – SMQ Broad

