#### 9.4 Deaths

The frequency (number and percentage) of subjects in the SAS who died and who died within 30 days after last dose of study treatment as well as the reason for death, will be tabulated:

- All deaths
- Deaths within 30 days after last dose of study treatment
- Reason for death

In addition, date and cause of death will be provided in individual participant data listing together with selected dosing information (study treatment received, date of first / last administration, dose) and will include the following information:

- AEs with fatal outcome (Listing of PTs of AEs with outcome=Fatal, as well as AEs of Grade 5)
- Flag for death within 30 days of last dose of study treatment.
- Flag for death related to COVID-19

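### SAP 6.4 ends the treatment-emergent window at new anti-cancer therapy for serious as well as nonserious events, so some SAEs the protocol still collects within 30 days of last dose reach no TEAE table

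*SAP*

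**What the plan says.** The SAP fixes the window in two steps. Section 6.4 sets the on-treatment period from "the first dose of study treatment through minimum (30 days + last dose of study treatment, start day of new anti-cancer therapy" and makes it the default: "Safety endpoints will be summarized based on the on-treatment period, unless otherwise specified". Section 9.3 then states that "Treatment Emergent Adverse Events (TEAEs) are those events with onset date occurring during the on-treatment period". It makes no exception for events that are serious, related or fatal. All the AE summary tables in 9.3 are TEAE tables, including those for serious events, treatment-related serious events, events leading to death, and treatment-related events leading to death.

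The protocol separates the two kinds of event. Section 13.5.3 sets active collection "through and including a minimum of 30 calendar days after the last administration of the study intervention". Under 13.5.4, once a new anti-cancer therapy begins, "the recording period for nonserious AEs ends at the time the new treatment is started", but "SAEs must continue to be recorded on the CRF during the above indicated active collection period". Section 13.1.2 likewise requires SAEs "within 30 days following the cessation of treatment, whether or not they are related to the study intervention" to be recorded, with no cut at new therapy. Section 12.3.1 plans incidence tables for SAEs and for related AEs and does not limit them to treatment-emergent events.

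Outside the TEAE tables, SAP 9.3 lists all AEs and AEs leading to death. SAP 9.4 tabulates all deaths, "Deaths within 30 days after last dose of study treatment", and the reason for death. It also lists deaths with the preferred terms of fatal and Grade 5 AEs.

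**The concern.** The SAP applies to every event a stopping rule that the protocol reserves for nonserious events, and it does not say that it does so. The usual reason for such a cut is to avoid charging study drug with the next drug's toxicity. That reason is sound for events nobody has attributed. It is weaker for a serious event that the investigator has judged related to TTI-621 or doxorubicin, because the SAP records causality for each study drug.

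Safety is a primary objective in both parts of the study, and the expansion cohorts are small. SAP 4.3.2 gives 31 patients planned in Cohort A, 18 enrolled in Cohort B and 13 in Cohort C. If the only SAE a patient had is omitted, the cohort's SAE rate moves by 1/31 = 3.2, 1/18 = 5.6 or 1/13 = 7.7 percentage points.

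**Working it through.** The point rests on definitions, and the plan states no figure to reproduce. The check is date logic.

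**Inputs.** Let L be the date of last dose and d the number of days from L to the start of new anti-cancer therapy. SAE collection runs to at least L + 30 (Protocol 13.5.3, 13.5.4). The TEAE window ends at min(L + 30, L + d) (SAP 6.4, 9.3). The documents do not give d, so the values below are assumptions.

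**Formula.** Days of required SAE collection outside the TEAE window = max(0, 30 − d).

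| d (assumed) | Days uncovered | Share of the 30 days |
|---|---|---|
| 7 | 30 − 7 = 23 | 77% |
| 14 | 30 − 14 = 16 | 53% |
| 21 | 30 − 21 = 9 | 30% |
| 28 | 30 − 28 = 2 | 7% |
| 30 or more, or no new therapy | 0 | 0% |

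**Example.** New therapy starts at L + 14 and an SAE begins at L + 20. Protocol 13.5.4 requires it on the CRF because 20 ≤ 30. SAP 6.4 closed the window at L + 14, so under 9.3 it is not a TEAE and enters no 9.3 summary table, whatever its attribution or outcome.

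**Where such an event does appear.**

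| Event in the gap | 9.3 TEAE tables | Other planned output |
|---|---|---|
| Non-fatal SAE, related or not | None | All-AE listing only; no separate SAE listing is planned |
| Fatal SAE | None | All-AE and fatal-AE listings; 9.4 deaths table and listing, with no relatedness row in the table |

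**What is not affected.** An event that began before new therapy and later became serious or fatal keeps its onset date and stays a TEAE. An AE with a wholly missing onset date is a TEAE by default, unless its stop date is known to precede first dose. For nonserious AEs the SAP cut agrees with Protocol 13.5.4.

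**With the window for SAEs run to L + 30 regardless of d**, the gap is 0 days for every d.

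**The case against.** The strongest defence is that this is a legitimate analysis choice. The protocol sections on AE recording govern collection, the protocol defines no treatment-emergent window, and Protocol 12.4 leaves analysis detail to the SAP. Collecting more than is tabulated is normal: AEs are collected from consent, yet pre-dose events are not TEAEs. The Safety Follow-Up Visit also uses an earliest-of rule, falling 30 + 5 days after last dose or before new therapy. This stands to the extent that a reader who infers a direct contradiction between protocol and SAP goes too far. It does not explain why events judged serious and related should have no incidence row, when Protocol 12.3.1 plans SAE and related-AE tables without that restriction.

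Four other stronger readings are tempting, and the documents do not support them.

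- **That the events are lost.** They remain in the listings, and the deaths are in 9.4.
- **That this rule makes the deaths outputs disagree.** Section 9.4 counts all deaths, while 9.3 counts AEs by onset date. The two would differ without the cut.
- **That a sizeable share of related toxicity is hidden, or that the loss differs by dose cohort.** If one assumes that 20% to 40% of patients start new therapy at day 21 or day 14, then 0.20 × 0.30 = 6% to 0.40 × 0.53 = 21% of the 30-day follow-up is uncovered. That is a share of days, not of SAEs. Per patient it is 0.20 × 9 = 1.8 to 0.40 × 16 = 6.4 days. Against about 365 days (the protocol's estimated 11 months of treatment plus 30 days) it is 0.5% to 1.8%. No document gives these shares or any difference by cohort.
- **That all treatment-related AEs should be counted to day 30.** Nonserious AEs are no longer recorded once new therapy starts, so a longer window for them would imply follow-up that did not happen.

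**Conclusion.** The point holds, limited to serious events. SAEs with onset after new anti-cancer therapy and within 30 days of last dose, including those attributed to study drug, must be collected but are left out of the serious, treatment-related serious and fatal TEAE tables. The uncovered span is 30 − d days for a patient who starts new therapy d < 30 days after last dose, and zero for everyone else. The documents give neither the number of such patients nor the number of events. The count is probably small, because the gap is a short stretch at the end of follow-up and only new onsets count. It is worth correcting because the cohorts are small, safety is a primary objective and the remedy is cheap. It does not put the trial's safety conclusions in doubt.

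**What to change.** Leave the definitions in SAP 6.4 and 9.3 in place and add, for serious AEs only (fatal ones included), rows or tables for:

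- SAEs;
- treatment-related SAEs;
- treatment-related fatal AEs;

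each with onset from first dose through last dose + 30 days regardless of new anti-cancer therapy. Footnote how many began after new therapy started. State the endpoint as last dose + 30 days, because the protocol's collection period is only a minimum and so gives no fixed end. Keep the current cut for nonserious AEs and laboratory shifts.

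The cost is a short SAP text change, one derivation flag and a few extra rows. No new data are needed, because Protocol 13.5.4 already requires these SAEs on the CRF. The downside is that some added events may be due to the next therapy. This includes some in the related rows, since Protocol 13.3 counts a possible relationship as related. The all-causality row may also pick up deaths from the malignancy, which Protocol 13.1.1 records as Grade 5 SAEs during active collection. The footnote and the unchanged TEAE tables alongside let a reader judge both.
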